- Immunosuppressant medications
 - Current or recent (<3 months) treatment with anti-neoplastic agents
 - Current or recent (<3 months) treatment with calcineurin inhibitors (tacrolimus, cyclosporine)
 - Current or recent (<3 months) treatment with mycophenolate mofetil
 - Current or recent (<3 months) treatment with monoclonal antibodies to B and T-Cells, anti-TNF, glucocorticoids, antimetabolities (azathioprine, 6-mercaptopurine)
- Neutropenia with absolute neutrophil count (ANC) <0.5 x 10⁹/L
- Active gastroenteritis due to infectious cause other than CDI
- Short gut syndrome
- Colostomy
- Ascites
- End-stage liver disease
- Untreated, in-situ colorectal cancer
- Irritable bowel syndrome
- Inflammatory bowel disease including Crohn's disease and ulcerative colitis
- Microscopic colitis including collagenous colitis and lymphocytic colitis
- Severe food allergy (anaphylaxis) that cannot be confirmed as having been excluded from a donor's diet within the five days prior to donation
- Anorectal disorder/severe rectal sphincter tone abnormality or inability to retain enema material
- Unable or unwilling to tolerate colonoscopy/sigmoidoscopy, colonoscopy prep, or enema for any reason at discretion of MD
- Severe underlying disease that the patient is not expected to survive for the subsequent 12 months at the discretion of the MD.
- Any conditions for which, in opinion of MD, the treatment may pose a health risk

Target enrollment and rationale

The longitudinal cohort sample size (n=150) was chosen to allow recruitment in a suitable time frame. Strong consideration will be given to resubmitting documentation including IND amendment and IRB ammendment for a larger sample size and/or prolonged follow-up at the completion of the study.

III. Design Methodology

IV. Therapeutic Administration: Fecal Microbiota Transplantation Protocol

Donor selection, laboratory screening, and monitoring

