1. Colonoscopy/sigmoidoscopy: If patients experience clinical non-response and require vancomycin/fidaxomicin within 6 weeks post-FMT, after a 10 day course subject may opt to undergo a second FMT via colonoscopy with an alternate donor at the physician's discretion. Subjects will be followed per protocol for duration of study.

2. Enema: If patients experience clinical non-response and require vancomycin/fidaxomicin within 6 weeks post-FMT, after a 10 day course subject may opt to undergo a second FMT via colonoscopy with an alternate donor at the physician's. Subjects will be followed per protocol for duration of study.

Withdrawal

- 1. All reasons for study withdrawal will be reported.
- 2. Classification of withdrawal:
 - Post-enrollment but pre-FMT
 - Post-FMT but lost to follow-up at:
 - o Day 3
 - o Week 6
 - o Month 6
 - \circ Month 12
 - All reasonable efforts will be exhausted to contact subjects, and data analysis will be based on the last available assessment.
 - Adverse event or serious adverse event mediating withdrawal
 - Rescind informed consent
 - Procedure-related ineligible patients
 - Patients undergoing colonoscopy/sigmoidoscopy and discovered to be ineligible due to newly discovered exclusionary criteria (eg. in-situ colorectal cancer). FMT will not be performed as part of this study and no data will be collected.

V. Study Observations and Measurements

Study Endpoints

Safety Endpoints

Safety will be assessed by short and long-term safety summaries classified into:

- 1. Serious Adverse Events (SAE)
- 2. Adverse Events (AE)
- 3. New medical conditions
- 4. Changes in pre-existing medical conditions

Efficacy Endpoints

Efficacy will be captured through:

- 1. Clinical cure rate of first FMT at 6-week follow-up
 - Colonoscopy
 - Sigmoidoscopy
 - Enema

2. Clinical cure rate of second FMT at 6-week follow-up, in patients with clinical non-response

- Colonoscopy/sigmoidoscopy non-response: Alternate donor FMT by colonoscopy
- Enema non-response: Alternate donor FMT by colonoscopy

Microbiome Endpoints

Sequencing data targeting the composition of the gut microbiome will be used to assess whether there are consistent microbial signatures associated with clinical cure, clinical non-response, or safety endpoints.

Data Collection

Case Report Forms will be utilized to capture and collect data (Appendix 4):

1. Baseline Assessment (Day 0 - Clinical Assessment)

Section 1: Clinical Evaluation

- Study patient identifier
- Date

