- Demographics: Age, sex, race/ethnicity
- Pre-existing medical conditions
- Concomitant medications
- Vital signs including height, weight, calculated body mass index (BMI)
- CDI History, including:
 - o Date of initial CDI diagnosis
 - Number of CDI recurrences since initial diagnosis
 - o Baseline clinical symptoms and severity related to CDI
 - CDI treatments received to date

Section 2: FMT Procedure

- Study patient identifier
- Date
- Description of FMT procedures, including:
 - Route of administration (colonoscopy/sigmoidoscopy or enema)
 - Location in colon where FMT delivered
 - Sedation (if applicable)
 - Prep quality (if applicable)
 - Findings of colonoscopy (if applicable)
- Dose
- Unit ID/Lot# of each treatment
- Expiration Date
- Storage Condition
- FMT retention time (if less than 1 hour)
- Immediate adverse events

2. Short-term assessment I (Day 3 – Telephone Assessment)

- Study patient identifier
- Date
- Any change in baseline clinical symptoms related to CDI
- Assessment of SAEs, including:
 - Any complications related to FMT administration
 - Any potential infectious complications such as transmissible enteric infections, sepsis, peritonitis, or bacteremia
 - Any non-serious newly diagnosed infections (specific organism and body site)

- Any new medical conditions / new medications with associated clinical course
- Any changes in pre-existing medical conditions with associated clinical course
- 3. Short-term assessment II (Week 6 Clinical Assessment)
 - Study patient identifier
 - Date
 - Vital signs including height, weight, calculated body mass index (BMI)
 - Any change in baseline clinical symptoms related to CDI including documentation of clinical cure or clinical non-response
 - Assessment of SAEs, including:
 - Any complications related to FMT administration
 - Any potential infectious complications such as transmissible enteric infections, sepsis, peritonitis, or bacteremia.
 - Any new non-serious diagnosed infections (specific organism and body site)
 - Any new medical conditions / new medications with associated clinical course
 - Any changes in pre-existing medical conditions with associated clinical course

4. Long-term assessment I (Month 6 – Telephone Assessment)

- Study patient identifier
- Date
- Self-reported height and weight, resulting calculated BMI
- Any recurrence of CDI with description of clinical course, including additional treatments received
- Assessment of any new SAEs

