- Any new medical conditions / new medications with associated clinical course
- Any changes in pre-existing medical conditions with associated clinical course

5. Long-term assessment II (Month 12 – Telephone Assessment)

- Study patient identifier
- Date
- Self-reported height and weight, resulting calculated BMI
- Any recurrence of CDI with description of clinical course, including additional treatments received
- Assessment of any new SAEs
- Any new medical conditions / new medications with associated clinical course
- Any changes in pre-existing medical conditions with associated clinical course

Data Analysis

Primary Study: Safety and Efficacy (Aims 1-3)

Safety endpoints will be collected with raw events and crude rates reported for overall cohort. Clinical cure rates will be calculated at each site. Both unweighted pooled clinical cure rates and weighted pooled clinical cure rates will be calculated with corresponding 95% confidence interval (CI) for overall study, as well as pre-defined

subgroups including: age, gender, modified Horn index, delivery modality, donor, retention time, site. Weighted pooled rates will be analyzed using the random effects model (DerSimonian-Laird method). Heterogeneity across sites will be assessed using the I² statistics and the Cochran Q test, where I² > 50% or Cochrane Q < 0.10 will be considered to indicate significant heterogeneity. Statistics will be performed using Stata SE 12.0 (StataCorp, College Station, TX).

Secondary Study: Microbiome (Aim 4)

DNA will be extracted from each frozen specimen collected from both donors and recipients. The V4 region of the 16S rRNA gene will be amplified using multiplexed bar-coded primers as previously described.²⁷ Up to 192 samples will be pooled onto a single lane of an Ilumina MiSeq for high-throughput sequencing. Quality trimmed and filtered sequence data will be clustered into Operational Taxonomic Units (OTUs) for computational analysis. Each recipient will receive an engraftment score based on their similarity (as quantified by the Jensen-Shannon Divergence) to the donor used in their FMT. Recipients will also be assessed for the long-term stability of their community and it's similarity to samples collected and previously published from both healthy and dysbiotic patients.

VI. Adverse Event Monitoring

We will capture both short and long-term safety profiles, including:

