 - Mild: Transient or intermittent episodes of unformed stools OR increase of ≤3 stools over baseline per 24-hour period
 - Moderate: persistent episodes of unformed to watery stools OR increase of 4-6 stools over baseline per 24-hour period
 - Severe: Bloody diarrhea OR increase of ≥7 stools per 24-hour period OR IV fluid replacement indicated

- Potentially Life Threatening: Life-threatening consequences (e.g. hypotensive shock)
- Nausea
 - Mild: Transient (<24 hours) or intermittent nausea with no or minimal interference with oral intake
 - Moderate: Persistent nausea resulting in decreased oral intake for 24-48 hours
 - Severe: Persistent nausea resulting in minimal oral intake for >48 hours OR aggressive rehydration indicated (intravenous fluids)
 - Potentially Life Threatening: Life-threatening consequences (e.g. hypotensive shock)
- Vomiting
 - Mild: Transient or intermittent vomiting with no or minimal interference with oral intake
 - Moderate: Frequent episodes of vomiting with no or mild dehydration
 - Severe: Persistent vomiting resulting in orthostatic hypotension OR aggressive rehydration indicated (intravenous fluids)
 - Potentially Life Threatening: Life-threatening consequences (e.g. hypotensive shock)

Long-term

The following long-term AEs and relevant details will be solicited:

- Gastrointestinal disorders
 - Inflammatory bowel disease
 - Irritable bowel syndrome
 - Celiac disease
 - Colon cancer
- Chronic infectious diseases (no therapy, outpatient, inpatient, ICU care)
- Autoimmune diseases
 - Inflammatory arthritis
 - Thyroid disease
 - Connective tissue diseases
 - Idiopathic thromobocytopenic purpura
- Metabolic disease
 - Diabetes Type 2 (diet controlled, oral hypoglycemic, insulin, uncontrolled/complication associated)
 - Metabolic syndrome (including obesity independently)
 - Non-alcoholic fatty liver disease
- Neuro-psychiatric disease
 - Multiple sclerosis
 - Depression/Anxiety
- Cardiovascular disease
 - Myocardial infarction (NSTEMI/STEMI)

- Stroke
- Cardiovascular related death

VI-C. Monitoring of Adverse Events

Each subject will be monitored for the occurrence of AEs, including SAEs. Each subject will be followed for safety monitoring at each follow-up interval.

- Subjects will be questioned at each follow-up interval regarding stool
 patterns, abdominal pain, fevers, and subjective well-being. First, subjects
 will be questioned about the possible occurrence of adverse events in a

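### New-onset rates for chronic conditions allowed at entry are taken over the whole cohort, and the visible plan has no matching Day 0 check that each condition was absent

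*Combined protocol and SAP*

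**What the plan says.** All references are to section 6 of the combined protocol and SAP.

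- Study Endpoints lists "New medical conditions" as the third safety endpoint and "Changes in pre-existing medical conditions" as a separate fourth.
- Data Analysis, Primary Study, gives the only rule for analysing them: "Safety endpoints will be collected with raw events and crude rates reported for overall cohort". It defines no set of subjects at risk for any condition. No rule says how a condition is established as absent before FMT.
- VI-B, Long-term, opens with "The following long-term AEs and relevant details will be solicited" and names conditions by body system. One entry reads "Metabolic syndrome (including obesity independently", so obesity counts in its own right.
- The Day 0 form, as summarised under Data Collection, carries the general item "Pre-existing medical conditions", together with medications, height, weight and BMI. The named list does not appear there. The case report forms in Appendix 4 were not available for review.
- VI-C begins each follow-up contact with a general question and moves to the solicited items after a positive answer. The follow-up section directs the assessment to what has changed since the previous contact.

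**The concern.** A subject who has type 2 diabetes at Day 0 cannot contribute a new diagnosis, yet stays in the denominator. For a condition common at entry, the reported new-onset rate is then lower than the rate among subjects who could develop it. The upper confidence limit is also lower than it should be, so the data look more reassuring than they are.

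There is a second, opposing problem. If the named list is used only after FMT, a long-standing condition that the general Day 0 history missed may surface at Month 6 or 12 and be entered as new.

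This matters because X. Potential Limitations acknowledges that there is no untreated arm. Each subject's own status before FMT is the only internal reference for deciding what is new. Long-term safety is specific aim 2, and VII-B names diabetes as a disease for which a recipient might acquire risk factors. VI-E also sends new or worsening conditions to the IRB and the sponsor and on to the FDA, so a misclassified case would travel beyond the final tables.

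**Working it through.** The plan states no prevalence, incidence or expected rate for these conditions, so there is no figure to reproduce. The cohort size is a feasibility choice: "The longitudinal cohort sample size (n=150) was chosen to allow recruitment in a suitable time frame".

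**Inputs**
- N = 150, from Target enrollment and rationale.
- p, the share of subjects with the condition at Day 0: assumed, 10 to 40%.
- I, the 12-month incidence among subjects free of it at Day 0: assumed, 2% or 5%.
- m, the share of prior cases not recorded at Day 0 and later reported as new: assumed, 0 to 20%.

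**Which listed conditions are affected.** The VI-B list was set against the exclusion criteria.
- Type 2 diabetes, obesity/metabolic syndrome, fatty liver, thyroid and other autoimmune disease, celiac disease and depression/anxiety are not excluded as diagnoses. Recent use of the listed immunosuppressants is an exclusion, which will remove some subjects with autoimmune disease.
- Inflammatory bowel disease and irritable bowel syndrome are excluded, so p = 0 for known disease.
- Myocardial infarction, stroke and cardiovascular death are events. A prior history does not take a subject out of risk.

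**Step 1: dilution.** Subjects at risk = N(1 − p), and expected new cases = I × N(1 − p). The crude rate over N is therefore I(1 − p). The zero-event one-sided 95% upper bound is 1 − 0.05^(1/n).

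| p | n at risk | crude ÷ at-risk rate | 3 events over n at risk | zero-event upper bound |
|---|---|---|---|---|
| 0% | 150 | 1.00 | 2.00% | 1.98% |
| 10% | 135 | 0.90 | 2.22% | 2.19% |
| 20% | 120 | 0.80 | 2.50% | 2.47% |
| 30% | 105 | 0.70 | 2.86% | 2.81% |
| 40% | 90 | 0.60 | 3.33% | 3.27% |

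The plan's rule gives the first row whatever p is. At p = 30%, three events are 3/150 = 2.0% (exact 95% CI 0.4 to 5.7%) under the plan's rule and 3/105 = 2.9% (0.6 to 8.1%) among those at risk.

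**Step 2: prior cases reported as new.** The crude rate becomes I(1 − p) + pm. At p = 30% there are 45 prior cases and 105 subjects at risk. True new cases are 105 × 0.02 = 2.1 or 105 × 0.05 = 5.25.

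| m | false new cases (45m) | crude rate, I = 2% | ratio to I | crude rate, I = 5% | ratio to I |
|---|---|---|---|---|---|
| 0% | 0 | 1.4% | 0.70 | 3.5% | 0.70 |
| 5% | 2.25 | 2.9% | 1.45 | 5.0% | 1.0 |
| 10% | 4.5 | 4.4% | 2.2 | 6.5% | 1.3 |
| 20% | 9.0 | 7.4% | 3.7 | 9.5% | 1.9 |

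These are upper figures for each m, because they take every missed case to be reported later as new.

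**Step 3: net direction.** Setting I(1 − p) + pm = I gives m = I. The two errors cancel only when the missed share happens to equal the incidence. Below that the crude rate is too low, and above it too high.

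**The case against.** The strongest reply is that this is a reporting refinement in a descriptive cohort.

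- **Baseline capture is broader than one history item.** Screening includes a medical interview and physical examination. Baseline tests include a liver panel and random glucose, and Day 0 records medications and BMI. Prior obesity can be identified from BMI, and treated diabetes or thyroid disease from medications. This stands: m may be small.
- **Follow-up is not clearly an item-by-item prompt.** A reader might infer that every subject is taken through the list after FMT. VI-C makes the solicited questions depend on a positive general answer, and follow-up is directed to changes since the last contact. That limits false new cases. It could also miss true ones, which is a further argument for asking the same questions each time.
- **Appendix 4 may hold a Day 0 checklist.** This cannot be checked. A checklist would ease the second error but leave the denominator as it is.
- **The dilution is small beside sampling error.** True at these event counts: the intervals 0.4 to 5.7% and 0.6 to 8.1% overlap heavily. But dilution is systematic and always lowers the estimate and its upper limit.
- **At-risk rates can be computed later from collected data.** True for the denominator, provided Day 0 status is right. A condition missed before FMT cannot be cleanly recovered afterwards.

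A reader might also infer that the plan commits to comparing these rates with matched population data. X. Potential Limitations says only that such data will be considered where possible, refers to serious adverse events, and states that this is not the primary aim.

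**Conclusion.** The point holds for the listed chronic conditions that are allowed at entry. On the stated rule, dilution alone understates their new-onset rate by the baseline prevalence: 10 to 40% in relative terms at an assumed prevalence of 10 to 40%. At 30%, three events read 2.0% instead of 2.9%, and the zero-event upper bound reads 1.98% instead of 2.81%. Misclassified prior cases act in the opposite direction. Because p, I and m are all assumptions, the net error cannot be signed or sized from the documents.

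A reader might extend this to the whole VI-B list or to the halting rule. The documents do not support that. Inflammatory bowel disease and irritable bowel syndrome are excluded at entry, so the safety-review trigger in VI-G, which specifies new inflammatory bowel disease, is not affected. The listed cardiovascular items can occur whatever the history. Nor do the documents show that missed prior cases would outnumber true new ones; they give no incidence for any listed disease.

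This is an inexpensive improvement worth making. It does not undermine the study.

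**What to change.** - **Day 0 form.** Before FMT, record each chronic condition on the VI-B long-term list as present or absent. If Appendix 4 already does this, say so in Data Collection.
- **Months 6 and 12.** Ask the same list at both contacts, whatever the answer to the opening general question.
- **Definition of new.** Record the onset or diagnosis date of each condition reported after FMT. Class onset before Day 0 as pre-existing.
- **Data Analysis.** Report each chronic condition's new-onset rate among subjects free of it at Day 0, beside the raw count and the overall-cohort rate. Keep worsening of an existing condition under the fourth safety endpoint, as now.

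The cost is a few minutes per subject, one checklist on the form and a short addition to Data Analysis. Denominators become somewhat smaller and intervals wider, for example 105 rather than 150 at an assumed 30% prevalence. The checklist needs to be in place before subjects are treated; the denominator can be settled at any time before analysis.

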1. FMT procedure-related adverse events from colonoscopy/sigmoidoscopy or enema (e.g. perforation, sedation related)

2. FMT material-related adverse events (e.g. transmissible infection, allergic reaction) 3. Short-term safety: Both solicited and unsolicited adverse events will be recorded by, telephone follow-up at Day 3 (+/- 2 days) and clinical assessment at Week 6 (+/- 2 weeks).

4. Long-term safety evaluations will focus on any new medical conditions/medications, which may be related or unrelated to FMT. This information will be elicited at the 6 month and 12 month follow-up telephone call and documented.

VI-A. Adverse Events Reporting

A. Definitions

1. Adverse Event (AE)

An AE is any untoward medical occurrence in a patient or study subject administered FMT that does not necessarily have a causal relationship with this treatment. An AE can therefore be any unfavorable and unintended sign (including an abnormal laboratory finding), symptom, or disease temporally associated with the use of a FMT, whether or not related to the FMT.

• AEs may be new events or may be pre-existing conditions that have become aggravated or have worsened in severity or frequency.

• AEs may be clinically significant changes from baseline in physical examination, laboratory tests, or other diagnostic investigation (e.g. laboratory results, radiographic findings).

Pregnancy is not an AE; however, if a female subject becomes pregnant during the conduct of the study, the Investigator will notify Sponsor who is responsible for notifying the FDA.

2. Serious Adverse Event (SAE)

A serious adverse event is any adverse experience occurring during or after FMT that results in any of the following outcomes:

• Death

• Life-threatening experience

Note: An adverse event or suspected adverse reaction is considered "life-threatening" if, in the view of either the Investigator or Sponsor, its occurrence places the patient or subject at immediate risk of death. It does not include an adverse event or suspected adverse reaction that, had it occurred in a more severe form, might have caused death.

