• Requires inpatient hospitalization or prolongation of existing hospitalization Note: Adverse events requiring hospital admissions that are less than 24 hours in duration do not meet this criterion. A scheduled hospitalization for a pre-existing condition that has not worsened during participation in the study does not meet this criterion. Pre-planned hospitalizations for an elective medical/surgical procedure or routine check-ups do not meet this criterion. Admission for CDI relapse will not be included in this definition.

- Results in persistent or significant disability or incapacity
- Results in a congenital anomaly or birth defect

• Results in an important medical event

Note: Important medical events are those that may not be immediately life threatening or result in death or hospitalization but may jeopardize the patient or may require intervention to prevent one of the outcomes listed in the definition above.

3. Planned Hospitalization

A hospitalization planned prior to FMT is to be considered a therapeutic intervention and not the result of a new SAE. If the hospitalization or procedure is executed as planned, it will be recorded in the subject's medical history or procedures. However, if the event/condition worsens during the study, it must be reported as an AE.

4. Adverse reaction

An adverse reaction means any adverse event caused by FMT. Adverse reactions are a subset of all suspected adverse events for which there is reason to conclude that FMT caused the event.

5. Suspected Adverse Reaction

Suspected adverse reaction means any adverse event for which there is a reasonable possibility that FMT caused the adverse event. For the purposes of IND safety reporting, 'reasonable possibility' means there is evidence to suggest a causal relationship between FMT and the adverse event. A suspected adverse reaction implies a lesser degree of certainty about causality than adverse reaction, which means any adverse event caused by a therapy.

6. Unexpected

An adverse event or suspected adverse reaction is considered "unexpected" if it is not listed in the Investigator brochure or is not listed at the specificity or severity that has been observed; or is not consistent with the risk information described in the general investigational plan or elsewhere in the current application.

VI-B. Solicited Adverse Events

Short-term

The following short-term AEs and their associated intensities will be solicited:

- Fever
 - Mild 37.7-38.6°C

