 generalized way, such as, "How have you been feeling since your last
 visit?" Subsequent solicited questions and relevant details will be asked if
 there is a positive response. Site Investigators will be contacted by study
 representative if there is a suspected or reported AE
- Subjects having AEs will be monitored with relevant clinical assessments and laboratory tests, as determined by the site Investigator
- AEs, actions taken as a result of AEs, and follow-up results will be recorded as well as in the subject's source documentation. Follow-up laboratory results should be filed with the subject's source documentation
- Subjects will receive a follow-up phone call 6 and 12 months post-FMT to record any SAEs, new medical conditions/new medications, or changes in pre-existing medical conditions

VI-D. Assessment of Adverse Events

1. Assessment of Severity

The severity of AEs will be assessed according to the following definitions: •Mild: the AE is noticeable to the patient and/or the Investigator, but does not interfere with routine activity

•Moderate: the AE interferes with routine activity, but responds to symptomatic therapy or rest

•Severe: the AE significantly limits the patient's ability to perform routine activities despite symptomatic therapy

2. Assessment of Causality

The Investigator must assess the relationship of any AE (including SAEs) to FMT, as related or not related, based on clinical judgment and using all available information, and may include consideration of the following factors:

• Possible alternative causes of the AE, including the disease under treatment, pre-existing conditions, concomitant use of other drugs, and presence of environmental or genetic factors

- The temporal association between FMT exposure and onset of the AE
- Whether the manifestations of the AE are consistent with known actions or theoretical toxicity of FMT

The causal relationship between FMT and the AE will be assessed using one of the following categories:

Not Related: An AE is not associated with FMT if:

• Temporal relationship is lacking (e.g., the event did not occur within a reasonable time frame following administration of FMT); or

• Other causative factors more likely explain the event (e.g. pre-existing condition, other concomitant treatments);

Related: An AE is attributed to FMT if:

• There is a positive temporal relationship (e.g. the event occurred within a reasonable time frame following FMT); and

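### Section VI-C asks the solicited adverse-event questions only after a positive answer to a general question, which contradicts VI-B and may under-count short-term non-serious events.

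*Combined protocol and SAP*

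**What the plan says.** Three parts of section 6 describe how adverse events are collected.

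- **VI, item 3 (short-term safety).** "Both solicited and unsolicited adverse events will be recorded by, telephone follow-up at Day 3" and again at the Week 6 clinical assessment. No condition is attached.
- **VI-B (Solicited Adverse Events).** "The following short-term AEs and their associated intensities will be solicited". Eleven symptoms follow, each with graded intensities. The long-term list opens the same way: "The following long-term AEs and relevant details will be solicited". Neither list is conditional.
- **VI-C (Monitoring of Adverse Events).** At each follow-up, subjects are questioned on stool "patterns, abdominal pain, fevers, and subjective well-being". The same bullet says the interview begins with a general question about how the subject has felt since the last visit. It continues: "Subsequent solicited questions and relevant details will be asked if" "there is a positive response". What counts as a positive response is not defined.

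The Data Collection lists in section V for Day 3 and Week 6 include "Any change in baseline clinical symptoms related to CDI" and, under the serious adverse event heading, "Any complications related to FMT administration". They also cover infections, new conditions or medications, and changes in existing conditions. They do not reproduce the VI-B symptom list.

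**The concern.** A solicited event is one that every subject is asked about by name. If the question is put only to subjects who have already volunteered something, the event is in effect spontaneously reported, and the distinction that VI item 3 draws between solicited and unsolicited events loses its meaning. A subject who has mild nausea but answers that all is well would never be asked about nausea.

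This matters for three reasons:

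- Adverse events are one of the four safety endpoint classes in section V, and Data Analysis reports them as raw counts and crude rates for the whole cohort. A missed event lowers the reported rate directly. The rule in VI-E that all events be recorded cannot recover one that nobody elicited.
- The Introductory Statement faults earlier studies because their adverse events were volunteered, not looked for. VI-C partly restores that weakness.
- The trigger is undefined. Study representatives at four initial sites, with more possible, could apply it differently.

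**Working it through.** The plan gives no figure to reproduce. The check sets VI-B against everything the text says is asked of every subject.

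**Input 1: the VI-B short-term list.** Fever, chills, fatigue/malaise, anorexia, abdominal pain, bloating, gas, constipation, diarrhea, nausea, vomiting. Total = 11.

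**Input 2: the topics VI-C raises with everyone.** Stool patterns, abdominal pain, fevers, subjective well-being.

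| VI-C topic | VI-B items covered | Count |
|---|---|---|
| Fevers | Fever | 1 |
| Abdominal pain | Abdominal pain | 1 |
| Stool patterns | Diarrhea, constipation | 2 |
| Subjective well-being (generous reading) | Fatigue/malaise | 1 |
| **Total, generous** | | **5** |
| **Total, strict (well-being covers no named symptom)** | | **4** |

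**Items without an unconditional prompt by name.**

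- Generous: 11 − 5 = 6 (chills, anorexia, bloating, gas, nausea, vomiting); 6/11 = 54.5%.
- Strict: 11 − 4 = 7 (the same six plus fatigue/malaise); 7/11 = 63.6%.

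**Input 3: other prompts that do not depend on a positive response.**

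- The Day 3 and Week 6 data lists name 0 of the six. The item on CDI symptoms does not reach them by name, because the Introductory Statement describes those symptoms as running from diarrhea to abdominal pain.
- The item on complications of administration sits under the serious-event heading.
- The new-medications item would catch a symptom only if it had been treated.
- The instruction that subjects contact the team about any adverse event (section IV, Baseline assessment and follow-up) relies on spontaneous reporting.

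**Direction.** Compared with asking everyone all 11 items, a rule that skips questions for some subjects can remove events from the count but cannot add any. Any effect on the crude rate is therefore downward.

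**Size.** The documents give neither the true frequency of these symptoms nor the chance that an affected subject responds positively to the open question. The following is purely an illustration with assumed inputs. Suppose one of the six symptoms occurs in 20% of the 150 subjects: 0.20 × 150 = 30.

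| Assumed share giving a positive response | Recorded count | Crude rate |
|---|---|---|
| 90% | 0.90 × 30 = 27 | 27/150 = 18% |
| 70% | 0.70 × 30 = 21 | 21/150 = 14% |
| 50% | 0.50 × 30 = 15 | 15/150 = 10% |

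The table shows how the mechanism works and does not estimate the loss in this study.

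**The case against.** The case for leaving this as a minor wording point runs as follows.

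- **VI-B may be the list and VI-C the interview order.** VI-C does not use the word only, and the conditional questions might be follow-up probes. VI-C's wording is indeed loose. But what it makes conditional is the solicited questions themselves, along with the details, so this reading leaves VI-B's promise unmet.
- **The trigger may be wider.** A positive answer on stool, pain, fever or well-being might also open the list. That would shrink the gap. A subject who reports nothing under those topics would still not be asked the six items, and the text ties the condition most naturally to the general question.
- **Other safeguards exist.** The Day 0 form records immediate adverse events, and VII-E says anticipated and unanticipated events will be monitored at each contact. In the small randomized trial of duodenal infusion summarized in section 9, minor gastrointestinal symptoms occurred on the day of infusion and resolved within 3 hours, so Day 0 capture could matter. These provisions help, but none names the six symptoms or removes the condition.
- **The forms may settle it.** Section V makes the Appendix 4 case report forms the collection instrument, and they are not in the available text. This is the strongest point. A full checklist there would make the practical effect small, although VI-C would then contradict the forms.
- **Little depends on it.** The SA1 and SA2 hypotheses concern related serious events, Potential Limitations puts the focus on serious events, and the halting triggers do not rest on these symptoms. This limits the importance of the point and is accepted.

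It is also true that 6 of 11 is a share of list items, not of events.

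**Conclusion.** The point holds and should be fixed. VI-C conflicts with VI-B and with VI item 3. As written, it leaves 6 of 11 short-term symptoms (55%), or 7 of 11 (64%) on the strict reading, without an unconditional prompt by name. Any resulting bias in the crude rate of short-term non-serious adverse events is downward.

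The number of missed events cannot be determined from the documents. The conclusion that under-counting may occur assumes that staff follow VI-C literally and that the Appendix 4 forms do not prompt every item. If the forms do, the remaining problem is an inconsistency between the protocol text and the forms.

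Serious events, new conditions and changes in existing conditions have their own unconditional items and are little affected. No material bias is shown for the long-term list. Confidence is moderate, mainly because the forms could not be seen.

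**What to change.** In VI-C, remove the clause that makes the solicited questions depend on a positive response. Keep the open question first so that unsolicited events are still volunteered. Then ask every subject each of the 11 VI-B short-term items at Day 3 and Week 6, recording yes or no and, where present, the VI-B intensity. Confirm that the Appendix 4 forms match. Reading out the VI-B long-term list at Months 6 and 12 is optional and would serve consistency only.

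The cost is one sentence of protocol text, a check of the forms and, by my estimate, a few minutes per contact at Day 3 and Week 6. The reported rate of non-serious events may come out somewhat higher, as expected when symptoms are actively sought.
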